2.2. Secondary endpoints

2.2.1. At week 192 :

- a. Cumulative HBsAg loss.
- b. HBeAg loss.
- c. HBsAg seroconversion.
- d. HBeAg seroconversion.
- e. ALT normalization (males \leq 30 U/L, females \leq 20 U/L).
- f. ALT \leq 38 U/L (males), \leq 25 U/L (females) corresponding to approximately 1.25 xULN.
- g. HBV DNA $<$ 1000 IU/mL.
- h. HBV DNA $<$ 20 IU/mL (Lower limit of quantification [LLOQ] of COBAS Ampliprep/COBAS TaqMan HBV v2.0 test).
- i. Absence of detectable antiviral drug-resistance HBV mutations.
- j. Sustained HBV DNA $<$ 1000 IU/mL

2.2.2. Sustained end of follow-up responses at week 240

- a. Cumulative HBsAg loss.
- b. HBeAg loss.
- c. HBsAg seroconversion.
- d. HBeAg seroconversion.
- e. ALT normalization (males \leq 30 U/L, females \leq 20 U/L).
- f. HBV DNA $<$ 1000 IU/mL.
- g. HBV DNA $<$ 20 IU/mL (LLOQ of COBAS Ampliprep/COBAS TaqMan HBV v2.0 test).

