2.2.3. Sustained off treatment (36 and 48 weeks after end of treatment) responses

- a. ALT \leq 38 U/L (males), \leq 25 U/L (females) corresponding to approximately 1.25 xULN.
- b. HBV DNA $<$ 1000 IU/mL.
- c. HBV DNA $<$ 1000 IU/mL AND ALT \leq 38 U/L (males), \leq 25 U/L (females) corresponding to approximately 1.25 xULN.
- d. HBV DNA $<$ 20 IU/mL (LLOQ of COBAS Ampliprep/COBAS TaqMan HBV v2.0 test).

2.2.4. Sustained off treatment (36 and 48 weeks after end of treatment) responses in participants with low end of treatment HBsAg levels ($<$ 2000 IU/mL) versus participants with high end of treatment HBsAg levels (\geq 2000 IU/mL)

- a. Cumulative HBsAg loss.
- b. HBeAg loss.
- c. HBsAg seroconversion.
- d. HBeAg seroconversion.
- e. ALT normalization (males \leq 30 U/L, females \leq 20 U/L).
- f. HBV DNA $<$ 1000 IU/mL.
- g. HBV DNA $<$ 20 IU/mL (LLOQ of COBAS Ampliprep/COBAS TaqMan HBV v2.0 test).

2.2.5. Sustained off-treatment (36 and 48 weeks after end of treatment) responses in participants with a substantial drop of HBsAg levels (\geq 1 log from baseline to end of treatment) versus participants who did not have substantial drop of HBsAg levels ($<$ 1 log from baseline to end of treatment)

- a. Cumulative HBsAg loss.
- b. HBeAg loss.
- c. HBsAg seroconversion.
- d. HBeAg seroconversion.
- e. ALT normalization (males \leq 30 U/L, females \leq 20 U/L).
- f. HBV DNA $<$ 1000 IU/mL.
- g. HBV DNA $<$ 20 IU/mL (LLOQ of COBAS Ampliprep/COBAS TaqMan HBV v2.0 test).

2.2.6. Sustained off-treatment (36 and 48 weeks after end-off treatment) responses in participants with end of treatment HBsAg level $<$ 2000 IU/mL and HBV DNA below 1000 IU/mL versus participants with end of treatment HBsAg levels \geq 2000 IU/mL and HBV DNA \geq 1000 IU/mL

- a. Cumulative HBsAg loss.
- b. HBeAg loss.

- c. HBsAg seroconversion.
- d. HBeAg seroconversion.
- e. ALT normalization (males \leq 30 U/L, females \leq 20 U/L).
- f. HBV DNA $<$ 1000 IU/mL.
- g. HBV DNA $<$ 20 IU/mL (LLOQ of COBAS Ampliprep/COBAS TaqMan HBV v2.0 test).

2.2.7. Treatment failure- Cumulative rates of primary nonresponse, partial virologic response and confirmed virologic breakthrough

2.2.8. Rate of discontinuation of treatment due to adverse events.

2.2.9. Rates of adverse events and serious adverse events.

3. Study design

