6.14.2. Criteria for treatment reinitiation in the Post-Treatment Follow up Period

Tenofovir DF will be restarted for any one of the following:

- Any one of the three criteria: INR ≥ 1.3 , total bilirubin ≥ 3.0 mg/dL or direct bilirubin ≥ 1.0 mg/dL, regardless of HBV DNA or ALT level.
- Any clinical decompensation, regardless of HBV DNA or ALT level.
- HBV DNA $\geq 10,000$ IU/mL and ALT > 1000 U/L (male or female) (i.e. only one ALT value > 1000 U/L is needed to qualify).
- HBV DNA $\geq 10,000$ IU/mL and ALT ≥ 300 U/L for males, ≥ 200 U/L for females. A total of one HBV DNA $\geq 10,000$ IU/mL and any three ALT values ≥ 300 U/L (male) or ≥ 200 U/L (female) over the 4-week (or longer) time frame are needed to qualify. Treatment will be resumed if the third ALT remains ≥ 300 U/L (male) or ≥ 200 U/L (female).
- HBV DNA $\geq 10,000$ IU/mL and ALT ≥ 150 U/L for males or ≥ 100 U/L for females. A total of one HBV DNA $\geq 10,000$ IU/mL and any three ALT values ≥ 150 U/L (male) or ≥ 100 U/L (female) over the 12 week (or longer) time period are needed to qualify. Treatment will be resumed if the third ALT remains ≥ 150 U/L (male) or ≥ 100 U/L (female).
- HBsAg-positive and HBeAg-positive at week 192.
- HBsAg-positive, HBeAg-negative, and anti-HBe-negative at week 192

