8.1.2.1. Analyses of other secondary endpoints

Secondary endpoints for this clinical trial are listed in sections 2.2.1 – 2.2.9. These endpoints could be grouped into several different classes. The first group of endpoints we will deal with are binary endpoints characterized by the occurrence of some event by a fixed time point. These events include HBeAg loss, HBeAg seroconversion, HBsAg seroconversion, normalization of ALT, ALT \leq 1.25 X ULN, HBV DNA $<$ 1000 IU/mL, HBV DNA $<$ 20 IU/mL, absence of detectable antiviral drug-resistance HBV mutations, treatment discontinuation, and treatment failure. Analysis will be conducted separately for these events at the designated time points listed in sections 2.2.1-2.2.9

Proportion of such an event (e.g. proportion of HBeAg loss) between two treatment groups will be summarized using 95% confidence intervals and will be presented graphically by using bar charts. The rate of occurrence of an event between two treatment groups will be compared using a two-sided two-sample proportion test (chi-square test or Fisher's exact test as appropriate). We will also describe the treatment effects using relative risk of the event and corresponding 95% confidence interval. In order to take into account the stratification at randomization, we will use Mantel-Haenszel chi-square test. Comparison of rates of an event across two treatment groups adjusting for other baseline demographic, virological and clinical characteristics such as

age, race, genotype, HBeAg status, initial HBV DNA level, and baseline histology will be performed using multivariable log-linear (Poisson) regression, with HBsAg loss (Yes/No) as the outcome. The results will be presented as relative risks of the event and their 95% confidence intervals.

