The third group of variables consists of variables that are measured over time (longitudinal data) such as quantitative HBV DNA levels. For graphical representation over time, we will use spaghetti plots of original data (e.g. HBV DNA levels) and summarize the pattern of data across subgroups (e.g. genotype, treatment groups) over time by using means (for continuous outcome) or proportions (for binary outcomes). To determine the significance of change in continuous outcome over time across treatment group adjusting for other baseline and longitudinal participant characteristics, we will use mixed models if the data are normally distributed or generalized estimating equations (GEE) if deviation from normality is evidenced. These approaches simultaneously model the regression of the response variable on the independent variables and account for the correlated nature of the responses. Analyses using conventional regression methods could provide erroneous variance estimates and loss of statistical efficiency because of the conventional assumption that each response is statistically independent. As a result, invalid inferences could be made if the conventional approach were applied to these longitudinal data. A similar approach of analysis will be adopted (generalized linear mixed model or GEE) for longitudinal binary or count outcomes over time.

The results will be summarized using rate of change/odds ratio/relative risk over time and the corresponding confidence intervals. Interaction between treatment and participant characteristics will be investigated to assess the differential effect of treatments across subgroups of participants (e.g. genotypes).

Secondary endpoints that are defined within a specific subgroup will be analyzed only for participants in that subgroup. For example, sustained off treatment (36 and 48 weeks after end of treatment) responses will be assessed only among those whose treatment was discontinued at week 192.

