8.2. Missing data

Primary analyses will be performed using all enrolled participants (intention-to-treat analysis). For the primary analysis, the proportion of patients with HBsAg loss at the end of follow-up (week 240) will be estimated using the product limit (Kaplan-Meier) method which includes drop outs for as long as they are followed. Since our sample size estimation accounts for participants lost to follow up for various reasons, and due to randomization, the rate of missing is expected to be similar in the two treatment groups, we will also conduct the analysis of primary endpoint on the available cases. For this analysis, we will describe the treatment effects in terms of relative risks and 95% confidence intervals. In order to take into account the stratification at the randomization, we will use Mantel-Haenszel chi-square test. Comparison of rates of HBsAg loss across two treatment groups adjusting for other baseline demographic, virological and clinical characteristics such as age, race, genotype, HBeAg status, initial HBV DNA level, and baseline histology will be performed using multivariable log-linear (Poisson) regression, with HBsAg loss (Yes/No) as the outcome. The results will be presented as relative risks of HBsAg loss and their 95% confidence intervals.

In general, the procedure of missing outcome data will be handled as follows in statistical analyses. First, we will explore the pattern of missing data by comparing characteristics of participants with available data to those with missing data. For data missing completely at random (does not depend on observed outcome; MCAR) standard analytical techniques described earlier would produce unbiased results when the analysis is performed on the complete data. For the time-to-event data analyses, the analytical methods such as Kaplan-Meier method, log-rank test, and Cox proportional hazard model automatically accounts for MCAR drop-outs. However, in other cases, we will assume that the dropout depends on observed outcome and/or covariates (missing at random, MAR). For such scenarios, likelihood-based methods such as mixed models, generalized linear mixed models and logistic regression will provide unbiased inference. For GEE, we will draw inference using inverse-probability-weighting approach, with models fitted using the reciprocal of the estimated probability of missing as weights. The probability of missing will be estimated using logistic regression.

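### Off-treatment endpoints: the 2.2.6 comparator group is nearly empty under the plan's own stopping criteria, and HBV DNA and ALT responses have no scoring rule for participants who restart tenofovir

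*Combined protocol and SAP*

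**What the plan says.** **Endpoints.** Section 2.2.3 lists "Sustained off treatment (36 and 48 weeks after end of treatment) responses" for HBV DNA and ALT. Sections 2.2.4 to 2.2.6 repeat off-treatment responses by end-of-treatment subgroup. In 2.2.6 the groups are HBsAg <2000 IU/mL with HBV DNA <1000 IU/mL, and HBsAg ≥2000 with HBV DNA ≥1000. A separate set, 2.2.2, covers "Sustained end of follow-up responses at week 240" and is not confined to participants off drug.

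**Analysis.** Section 8.1.2.1 treats these as "binary endpoints characterized by the occurrence of some event by a fixed time point". It states: "We will also describe the treatment effects using relative risk of the event and corresponding 95% confidence interval". It restricts the set: off-treatment "responses will be assessed only among those whose treatment was discontinued at week 192".

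**Stopping.** Section 6.5.1 requires, among other criteria, HBV DNA <1000 IU/mL from week 156 or earlier through week 180. Any further results up to the week 192 visit are also considered.

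**Restarting.** Section 6.14.2 opens "Tenofovir DF will be restarted for any one of the following" and lists seven routes. Three need HBV DNA ≥10,000 IU/mL with raised ALT. Two rest on week 192 serology, for example "HBsAg-positive, HBeAg-negative, and anti-HBe-negative at week 192". The INR/bilirubin and clinical decompensation routes apply whatever the HBV DNA or ALT level. Under 6.14.3 the study supplies tenofovir to week 240, and ALT and HBV DNA are still measured.

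**Missing data.** Section 8.2 says that "the procedure of missing outcome data will be handled as follows in statistical analyses". It deals with drop-out and absent outcomes, and does not mention restarts.

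**The concern.** Response after stopping is one of the trial's two stated objectives, and these endpoints carry it.

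For 2.2.6, the rule that decides who may stop also rules out, almost entirely, the HBV DNA level that defines the comparator. A contrast with a handful of participants on one side cannot be interpreted.

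For 2.2.3 to 2.2.6, entry to the analysis depends on having been discontinued at week 192, not on having stayed off drug. A participant who relapsed, restarted and was resuppressed by week 228 or 240 has an observed value below the threshold. Scored at the fixed time point, that value is an off-treatment success. Non-response, exclusion and observed values are all open, and the choice could be made after the data are seen.

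**Working it through.** **Plan's own figure.** The plan gives no number for these endpoints. Its one computed figure is the primary sample size (5% v 15%, two-sided 5%, 80% power), which reproduces:

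n = [1.960√(2×0.10×0.90) + 0.842√(0.05×0.95 + 0.15×0.85)]² / 0.10² = (0.8315 + 0.3521)² / 0.01 = 140.1, so 141 per arm; 141/0.75 = 188 per arm, 376 in total.

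It is not in dispute. It serves below only as an upper bound: 376 × 0.75 = 282 participants retained.

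**2.2.6: who can be in each group.** Every participant in the set was discontinued at week 192, so under 6.5.1 had HBV DNA <1000 through week 180.

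- HBsAg <2000, HBV DNA <1000: close to the whole low-HBsAg group of 2.2.4.
- HBsAg ≥2000, HBV DNA ≥1000 (comparator): only those whose HBV DNA rose at about week 192, or who stopped outside the criteria, and who also had high HBsAg. The week 192 sample may be reported after the stopping decision, so a few are possible.
- HBsAg ≥2000, HBV DNA <1000: in neither group.
- HBsAg <2000, HBV DNA ≥1000: in neither group, and rare for the same reason as the comparator.

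Expected comparator size = D × b × h, over both arms. All three ranges are assumptions:

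- D, number discontinued at week 192: 100 to 282. The top is a bound, because cirrhosis and other criteria keep some participants on treatment.
- b, share with HBV DNA first ≥1000 at week 192: 1% to 5%.
- h, share of those with HBsAg ≥2000: 30% to 70%.

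Low: 100 × 0.01 × 0.30 = 0.3. Middle: 150 × 0.02 × 0.50 = 1.5. High: 282 × 0.05 × 0.70 = 9.9. Any stops outside the criteria would add to these.

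**Restart scoring, one arm.** Per 100 stoppers, let n be responders who never restarted, R restarters, and s the share of restarters below threshold when sampled. Then non-response = n; exclusion = 100n/(100 − R); observed values = n + R×s. Assume n = 50, R = 20, s = 0.85:

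- non-response: 50%
- exclusion: 50/80 = 62.5%
- observed values: 50 + 17 = 67%

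With R at 10 or 30, exclusion gives 50/90 = 55.6% or 50/70 = 71.4%.

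**Restart scoring, two arms.** Assume restart in 30 v 20 per 100 and s = 0.85. The result depends on what is held equal between arms:

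| Held equal | Non-response | Exclusion | Observed values |
|---|---|---|---|
| 45 of 100 stoppers respond without restarting | 45 v 45: 0 | 64.3 v 56.3: +8.0 | 70.5 v 62.0: +8.5 |
| 60% of non-restarters respond | 42 v 48: −6 | 60 v 60: 0 | 67.5 v 65.0: +2.5 |

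In both rows the handlings span 8.5 points, which is (30 − 20) × 0.85. Which handling shows no difference changes with the definition of true response.

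**The case against.** The strongest reply is that the heading already settles the matter: someone back on tenofovir is not off treatment, and 2.2.2 exists for week 240 status regardless of drug. That makes observed-value scoring the least natural reading, and this much stands. It does not close the gap. The heading fits exclusion as well as non-response, the two give different rates, and the only sentence defining the set turns on discontinuation at week 192. The relapse definitions in 6.14.1 are meant for data analysis but are not tied to these endpoints, and treatment failure in 2.2.7 does not include restart.

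A reader might infer more than the documents support:

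- **That the omission favours the arm with more restarts.** The two-arm table shows that this follows only if true response is defined as response without restart, which is the non-response score itself.
- **That 85% resuppression is documented.** The 80–90% in the Background concerns long-term treatment. Nothing supports one share, by post-treatment week 36 or 48, for limits as different as HBV DNA <1000, HBV DNA <20 and the ALT cut-offs.
- **That INR or bilirubin restarts are non-viral.** They apply at any HBV DNA level, so the route does not show the cause.
- **That Appendix 4 contradicts 8.1.2.1 by following early stoppers.** It is a visit schedule and does not define an analysis set.
- **That the 6.14.1 definitions are themselves defective because an early restarter may meet none of them.** This needs several conditions at once, and relapse is not a listed endpoint in 2.2.

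For 2.2.6, it is fair to say that the harm is limited, since 2.2.4 already compares HBsAg <2000 with ≥2000.

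**Conclusion.** Both points hold on the text and should be fixed before analysis.

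The 2.2.6 contrast does not work as written. Its comparator is nearly empty, not provably empty: about 0.3 to 9.9 participants over both arms under the assumed inputs. Most stoppers with high HBsAg would probably fall in neither group.

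The HBV DNA and ALT items in 2.2.3 to 2.2.6 lack a rule for restarters, and a literal reading counts on-drug suppression as off-treatment response. The choice can move a single-arm rate materially (50% to 67% in the assumed example). The documents give no restart or resuppression rate, so the size and direction of any effect on the arm comparison are not established.

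Confidence is high for the omission and for the 2.2.6 defect, and low for any particular bias. The primary endpoint and the sample size are unaffected.

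**What to change.** Change the analysis and endpoint wording only. The clinical stopping and restart rules stay as they are.

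1. **2.2.6.** Drop it, relying on 2.2.4; or redefine it with complementary groups that vary among week 192 stoppers. An example is HBsAg <2000 with HBV DNA <20 IU/mL against all other stoppers. Check group sizes without regard to arm first.
2. **8.1.2.1.** Add: a participant who resumed any anti-HBV therapy before the post-treatment week 36 (or week 48) sample is a non-responder, at that time point, for the off-treatment HBV DNA and ALT endpoints in 2.2.3 to 2.2.6.
3. **Reporting.** Tabulate restarts and their reasons by arm.
4. **Sensitivity analysis.** Repeat with a different handling, such as exclusion or observed values, without classing INR or bilirubin restarts as non-viral.

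Cost: no new visits or samples; the restart date and reason are needed for each participant. Reported off-treatment response rates may look less favourable. Non-response is one estimand choice among several, which is why the sensitivity analysis is needed.

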Thus, the advantages of nucleos(t)ide analogue therapy are the ease of administration, the lack of significant side effects and the consistent suppression of HBV DNA that can be achieved, particularly with the newer agents such as tenofovir DF and entecavir. While emergence of drug resistance can limit the efficacy of oral agents, a low rate of antiviral resistance (1% or less even with prolonged therapy for 4 to 5 years), is seen with entecavir and tenofovir DF, reflective of their greater potency and higher genetic barrier to resistance. As a consequence 80-90% of patients treated long-term with these agents achieve rates of marked suppression of HBV DNA levels and normal ALT levels. The advantage of peginterferon therapy is that it is administered for a limited period (6 to 12 months) and results in loss of HBsAg in a significant proportion of patients. Previous studies have shown that a one-year course of combination therapy of peginterferon and nucleos(t)ide analogue does not yield a higher response rate than a one-year course of either agent alone (21). However, these studies have been limited by the use of a nucleos(t)ide analogue with high risk of resistance (e.g. lamivudine) and a relatively short course of treatment. Thus, an obvious question is whether the combination of a limited course of peginterferon (6 or 12 months) with long-term therapy with a potent nucleos(t)ide analogue (tenofovir DF or entecavir for at least 4 years) will provide a higher rate of loss of HBsAg and ability to stop therapy without relapse. This clinical trial compares the efficacy of peginterferon plus a potent nucleotide analogue, tenofovir DF, for 24 weeks followed by monotherapy with tenofovir DF for a further 3.5 years to the efficacy of that same potent nucleotide analogue, tenofovir DF, given for a full 4 years. The primary measure of outcome will be HBsAg loss in serum 240 weeks after starting antiviral therapy.

2. Study objectives

To define the role of limited duration peginterferon alfa-2a in the presence of tenofovir for treating people with chronic hepatitis B by:

- Evaluating “off treatment” sustained responses following combination therapy consisting of peginterferon alfa-2a plus tenofovir DF versus tenofovir DF monotherapy.
- Comparing the on-treatment efficacy of initial treatment with combination therapy consisting of peginterferon alfa-2a plus tenofovir DF versus tenofovir DF monotherapy.

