6.5 End of Treatment (Week 192)

At week 192, all participants will complete the following:

1. Physical exam.
2. Assessment of adverse events, concomitant medications and adherence
3. Questionnaires (symptoms, quality of life, health behaviors, and fatigue)
4. Depression assessment.
5. Blood will be drawn for CBC, hepatic panel (including albumin, total protein, alkaline phosphatase), renal panel, serum uric acid, PT/INR, anti-HIV, qualitative HBeAg, anti-HBe, anti-HBs, HBsAg, and HBV DNA. A sample of blood will be

stored for eventual assessment of HBeAg and HBsAg concentration, precore/BCP analysis, and antiviral resistance testing.

6. A blood sample for storing serum and plasma for future research will also be drawn
7. Urinalysis and fasting urine creatinine and phosphate.
8. Ultrasound exam (if clinically indicated, per AASLD guidelines, done as standard of care).
9. Fibroscan if available and not performed at, or since, the week 180 visit

At week 192 (year 4), participants who meet study criteria for discontinuing therapy (section 6.5.1) will have treatment stopped.

6.5.1 Eligibility criteria for discontinuing treatment at week 192 (participants must meet all criteria)

Participants will be discontinued from treatment if they meet all of the following criteria as determined based on laboratory results at the week 180 visit and any additional test results and clinical assessment up until the week 192 visit:

1. HBV DNA <1000 IU/mL for the previous 24 weeks (i.e. starting at or before week 156 and continuing through week 180).
2. No cirrhosis (Ishak score 5 or 6) on baseline biopsy
3. Normal indices of liver function (CTP =5), albumin ≥3.8 g/dL, INR ≤1.3, direct bilirubin ≤0.5 mg/dL
4. No clinical evidence of decompensation
5. No clinical or radiologic evidence of portal hypertension
6. Platelet count ≥120,000/mm³
7. HBeAg-negative at baseline visit and confirmed at week 180, or HBeAg-positive at baseline visit with HBeAg loss at or before week 144 and confirmed at week 180. In either situation, there can be no HBeAg positive result at or after week 144.
8. HBsAg-negative (regardless of anti-HBe status), or if HBsAg-positive, HBeAg-negative and anti-HBe-positive at week 180

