Participants who do not meet criteria for discontinuing treatment will continue treatment with tenofovir DF until Week 240 or end of the study. Tenofovir DF for the period Week 192 to Week 240 will be provided by the study. Follow up visits and testing will continue every 12 weeks (204, 216, 228) to week 240 or end of the study. If tenofovir DF will be continued beyond Week 240 or end of the study, medication must be obtained per standard of care.

Participants who meet criteria for discontinuing treatment but continue treatment will have follow-up visits and testing per the schedule for participants who discontinue treatment. No study medications (Tenofovir DF) will be provided beyond Week 192 and any antiviral therapy must be obtained per standard of care.

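### The between-arm test of the 2.2.3 off-treatment HBV DNA and ALT responses uses only participants who stopped at week 192, so it is not a randomised comparison and leaves out any effect on the ability to stop.

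*Combined protocol and SAP*

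**What the plan says.** Section 2 lists first the evaluation of off-treatment "sustained responses following combination therapy consisting of peginterferon alfa-2a plus tenofovir DF versus tenofovir DF monotherapy". The Background asks whether adding a limited peginterferon course "will provide a higher rate of loss of HBsAg and ability to stop therapy without relapse".

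Section 2.2.3 defines the off-treatment responses at 36 and 48 weeks after treatment ends, in terms of HBV DNA and ALT. Section 8.1.2.1 restricts the analysis set: these "responses will be assessed only among those whose treatment was discontinued at week 192". The same section compares binary secondary endpoints between arms with a chi-square or Fisher test and a Mantel-Haenszel test for the strata. Section 8.1 applies p<0.05 to all analyses.

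Section 6.5.1 decides who stops. Criterion 1 requires "HBV DNA <1000 IU/mL for the previous 24 weeks". Criterion 7 admits those who were HBeAg-negative at baseline, or "HBeAg-positive at baseline visit with HBeAg loss at or before week 144 and confirmed at week 180". Criterion 8 requires HBsAg-negative status or, "if HBsAg-positive, HBeAg-negative and anti-HBe-positive at week 180". Criterion 2 is a baseline feature ("No cirrhosis (Ishak score 5 or 6) on baseline biopsy"). Participants who fail the criteria stay on tenofovir DF to week 240. Some who pass may also stay on treatment: "Participants who meet criteria for discontinuing treatment but continue treatment will have follow-up visits and testing" on the schedule used for those who stop.

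**The concern.** Criteria 1, 7 and 8 are responses observed up to about week 180, and the randomised treatment can change them. Whether an eligible participant then stops is a further post-randomisation step, and 5.1 describes no placebo injection. Randomisation therefore does not make the two groups of stoppers comparable.

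The Background's question has two parts: can the participant stop, and does the response hold afterwards? The stopper-only analysis conditions on the first part and tests only the second. If peginterferon brings more participants to eligibility, that gain enlarges the combination denominator and is never counted as a benefit. If the additional stoppers relapse more often than the rest, the combination arm can even look worse while more of its randomised participants end up off drug and in response.

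**Working it through.** **Does other text repair this?**

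- Intention-to-treat is stated for the primary analyses (8.1, 8.2), not for 2.2.3.
- The Mantel-Haenszel test and the regression models in 8.1.2.1 use stratification and baseline factors. These cannot remove selection on post-baseline response.
- Inverse-probability weighting in 8.2 is for missing outcomes in GEE, not for entry to the stopping group.
- Section 2.2.2 is not worded as limited to stoppers, but at week 240 it pools participants on and off tenofovir DF.
- Treatment discontinuation in 8.1.2.1 corresponds to 2.2.8, which concerns adverse events. No listed endpoint gives the proportion able to stop under 6.5.1.
- Sections 2.2.4 to 2.2.6 are also off-treatment endpoints, but they contrast HBsAg-defined groups, not arms.

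**Inputs.** The plan has no figure for this endpoint. Its sample size, in 8.3 (Sample size and power), reproduces: 5% versus 15% at 80% power gives 141 per arm, and 282/(1 − 0.25) = 376, or 188 per arm. It rests on the primary endpoint and does not change. All stopping and response rates below are assumptions. Stopping shares are of all randomised, so anyone lost before week 192 counts as not stopping.

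**Formulas.** Let s0, s1 be the shares stopping on monotherapy and combination, and c0, c1 the sustained response among stoppers.

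- Success among all randomised = s × c.
- Stopper-only RR = c1/c0.
- All-randomised RR = (s1 × c1)/(s0 × c0) = stopper-only RR × (s1/s0). The factor s1/s0 is what the restriction removes.

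| s0 vs s1 | c0 vs c1 | Stopper-only RR | All randomised | RR |
|---|---|---|---|---|
| 40% vs 40% | 50% vs 55% | 1.10 | 20.0% vs 22.0% | 1.10 |
| 40% vs 55% | 35% vs 35% | 1.00 | 14.0% vs 19.3% | 1.38 |
| 40% vs 55% | 35% vs 30% | 0.86 | 14.0% vs 16.5% | 1.18 |
| 40% vs 50% | 35% vs 30% | 0.86 | 14.0% vs 15.0% | 1.07 |
| 40% vs 60% | 35% vs 25% | 0.71 | 14.0% vs 15.0% | 1.07 |

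In the first row, with the same people stopping in both arms, there is no distortion.

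**What the last three rows require.** Suppose everyone who would stop on monotherapy would also stop on combination, with sustained response a0 and a1 in the two arms. Let q be the response in the extra combination stoppers. Then c1 = [s0 × a1 + (s1 − s0) × q]/s1. With a0 = a1 = 35%:

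- 55% stopping, 30% sustained: q = (0.165 − 0.140)/0.15 = 16.7%
- 50% stopping, 30% sustained: q = (0.150 − 0.140)/0.10 = 10%
- 60% stopping, 25% sustained: q = (0.150 − 0.140)/0.20 = 5%

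**When the stopper-only comparison favours monotherapy.** This happens when q < a0 − s0 × (a1 − a0)/(s1 − s0).

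- If a1 = a0, any q below a0 is enough, although the gap is small when q is close to a0.
- With s0 = 40%, s1 = 60%, a0 = 50%, a1 = 55%, the threshold is 0.50 − 0.40 × 0.05/0.20 = 40%. At q = 20%, stoppers show 50.0% vs (0.22 + 0.04)/0.60 = 43.3%, while all randomised show 20.0% vs 26.0%.
- With s1 = 45% and a1 = 60%, the threshold is 0.50 − 0.40 × 0.10/0.05 = −30%, so no reversal is possible.

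**The case against.** The case on the other side has four parts.

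*Scope.* A reader might infer that the plan cannot answer its off-treatment objective at all. The documents do not support that. HBsAg loss, the first half of the Background's question, is the primary endpoint and is analysed in all randomised participants at week 240. The off-treatment aim is first in Section 2 but second in the Synopsis. The gap is the HBV DNA and ALT responses of 2.2.3. This stands, and it limits the point.

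*Reversal.* A reader might also infer that the stopper-only analysis will understate or reverse a benefit. The documents give no rates from which to say so, and the reversing rows above need response as low as 5% to 17% in the extra stoppers. In the 35% versus 30% case, 0.40 × 188 ≈ 75 and 0.55 × 188 ≈ 103 stoppers give a difference of −5 points with a 95% interval of about −19 to +9. The all-randomised difference has z of about 0.7. Neither analysis would detect an effect of that size, although bias does not depend on significance.

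*Unequal stopping.* The Background's HBeAg-loss rates, 12–24% versus 30–35%, differ by 6 to 23 points (30 − 24 and 35 − 12). They are one-year figures, and the same paragraph says longer nucleos(t)ide treatment may reach the peginterferon rates. Criterion 7 allows until week 144 and needs HBeAg loss only from those positive at baseline. If half were positive (an assumption), a 15-point stopping gap by this route needs 15/0.5 = 30 points of HBeAg loss. Both arms receive tenofovir DF and the Background expects marked suppression in 80–90%, so criterion 1 may separate the arms little. Unequal stopping is plausible, not established.

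*Purpose.* Durability among those withdrawn is a legitimate question, and the plan is open that the set is a subgroup. That justifies keeping the table. It does not make the comparison between arms a randomised one.

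**Conclusion.** The point holds for the between-arm test of 2.2.3. Its analysis set is defined by post-randomisation response and by whether eligible participants stop, nothing in the plan corrects for this, and no all-randomised analysis counts stopping and staying in response.

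The size and direction of any bias are unknown. If combination lets more participants stop, the restriction removes a factor s1/s0 from the relative risk. Under the assumed 40% versus 55% that factor is 0.55/0.40 = 1.38. A change of sign is possible but not expected: it requires both unequal stopping and sufficiently poorer response in the extra stoppers. The primary analysis and the 376 sample size are unaffected. This should be changed, but it does not undermine the trial's main result.

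**What to change.** In 8.1.2.1, make the between-arm analysis of 2.2.3 a comparison of all randomised participants, using the Mantel-Haenszel test already planned.

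- **Success:** treatment stopped at week 192 under 6.5.1, and the 2.2.3 limit met while off treatment at 36 and 48 weeks.
- **Not achieving it:** participants who were ineligible, and those who were eligible but continued treatment.
- **Losses:** state how participants lost before week 192 or during follow-up are scored. The plan expects about 25% loss, so this matters. One option is to count them as not achieving success, with a missing-data sensitivity analysis under 8.2.
- **Beside it:** report by arm, among all randomised, the proportion eligible to stop and the proportion who stopped. The composite still depends on the decision to continue, and these figures make that part visible.
- **Stopper-only analysis:** keep it as a descriptive, non-randomised summary of durability after withdrawal.

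The cost is SAP wording and an added table from data already collected. No visit, treatment or stopping rule changes. There are two downsides. Response rates will be lower, partly because participants with cirrhosis on the baseline biopsy cannot succeed. The composite also measures success of the whole strategy (being able to stop and staying in response) rather than durability alone.
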